4.7.2. Health Outcomes

Item-level missingness is dealt with as per the instrument developer's instruction.

4.7.2.1. EQ-5D-Y

EQ-5D-Y analyses will be guided by Efficacy estimand. The EQ-5D-Y is a standardized generic measure of health status developed by the EuroQoL Group. The EQ-5D-Y consists of the EQ-5D-Y descriptive 3-level system and the EQ VAS. The analysis for the PRO measures (EQ-5D-Y VAS and EQ-5D-Y index scores only if available) will be according to the efficacy estimand with an MMRM as described in Section 4.1.5.1 for the change in PRO score from baseline to Week 52 using the EAS2.

The EQ-5D-Y index score will be analyzed if it is available. Patient responses by EQ-5D-Y domains (mobility; looking after myself; doing usual activities; having pain or discomfort; feeling worried, sad, or unhappy) will also be descriptively examined. The above analyses will be calculated and reported for age 10 to 14 years old, 15 to <18 years old, and all ages combined group. Please refer to the EQ-5D-Y User's Manual for details about scoring are available in the EQ-5D-Y user guide at EuroQoL Research Foundation [https://euroqol.org/publications/user-gfor appropriate descriptive reporting examples, VAS, and how to handle missing data.

4.7.2.2. Pediatric Quality of Life

The 23-item PedsQL 4.0 Generic Core Scales were designed to measure the core dimensions of health as delineated by the (Varni et al. 2019), as well as role (school) functioning. The 2 versions used are for children (ages 8 to 12) and for teens (ages 13 to 18) (Varni et al 2023).

The PEDS-QL 3.2 Diabetes Module is a diabetes-specific health-related quality of life measurement instrument that includes 33 items comprising 5 dimensions for ages 8 and older. Higher scores indicate lower problems.

For the PEDS-QL generic and diabetes scales, transformation of scores are needed as indicated by the scoring manual. Items are scored on a 5-point Likert scale from 0 (Never) to 4 (Almost always). Items are then reversed scored as follows: 0=100, 1=75, 2=50, 3=25, 4=0. The dimension scores and the summary scores are calculated by summing the transformed scores of the items divided by the number of items answered. Moreover, for both the PEDS-QL generic and diabetes scales, if more than 50% of the items in the scale are missing, then the Scale Scores should not be computed. If 50% or more items are completed, mean of the completed items in a scale will be used to impute the missing scores. Refer to the PEDS-QL scoring manual to appropriately score all the dimensions, subscales, and total scores.

The analysis for the PRO measures (PEDS-QL Diabetes 3.2 and PEDS-QL 4.0 [generic scale]) will be analyzed according to efficacy estimand using MMRM, as described in Section 4.1.5.1, for the change in score from baseline to Week 52 using EAS2. Baseline data and each postbaseline visit scores will be calculated and reported for age 10 to 14 years old, 15 to <18 years old, and all age combined group.

The analyses will cover the total scores, all subscale scores, and dimensions.

Dimension Items per for PedsQL 4.0 Generic Core module:

Dimensions	Number of Items
Physical Functioning	8
Emotional Functioning	5
Social Functioning	5
School Functioning	5
Summary Scores	Items per Summary Score
Psychosocial (Emotional functioning, social functioning and School functioning)	15
Physical Health (Physical Functioning)	8
Total	23

Dimension Items per for PEDS-QL Diabetes 3.2 module:

Dimensions	Number of Items
Diabetes symptoms	15
Treatment I	5
Treatment II	6
Worry	3
Communication	4

4.7.3. Subgroup Analyses

Efficacy subgroup analyses will be guided by the treatment-regimen estimand in FAS for the primary endpoint at Week 30. Primary multiple imputation method will be used to impute for missing data (Section 4.1.6) consistent with the primary analysis model. The 2-way interaction of treatment-by-subgroup will be evaluated to assess an interaction in the treatment effect with the subgroup levels. Significance will be evaluated at 2-sided alpha of 0.1. The treatment differences between pooled tirzepatide and placebo for each level of subgroup will be presented.

The following subgroup analyses for mean change in HbA1c from baseline to Week 30 will be considered. This list is not necessarily all-inclusive:

- age group (10 to 14 years, or 15 to <18 years)
- race
- ethnicity
- region (US and non-US)
- sex
- duration of diabetes (<median and ≥median)
- baseline BMI (<median and ≥median)
- baseline body weight (<median and ≥median)

- Baseline antihyperglycemic medications use of
 - o Metformin only or
 - o Basal Insulin only, or
 - o Metformin and basal insulin
- baseline HbA1c ($\leq 8.0\%$ or > 8.0% [≤ 64 , > 64 mmol/mol]).

Safety subgroup analyses will also be conducted based on age group, race, and sex for the most frequently reported TEAEs (occurring in \geq 5% patients overall) using SS1.

Other analyses may include analyses of assessments, which are not defined as endpoints, that need to be prespecified and not necessarily be reported in the clinical study report such as, but not limited to, immunogenicity, biomarkers, population PK.

4.7.4. Pharmacokinetics Statistical Inference

All PK/PD analyses will be performed by Lilly or its designee and documented in a separate analysis plan.

4.8. Interim Analysis

No interim analyses of efficacy for early termination are planned for this study. An external DMC will have the responsibility to review unblinded interim analysis results to monitor the safety of the participants in the study.

If an unplanned interim analysis is deemed necessary, the appropriate Lilly medical director, or designee, will be consulted to determine whether it is necessary to amend the protocol.

Unblinding details are specified in a separate unblinding plan document.

4.9. Changes to Protocol-Planned Analyses

Refer to revision history.

5. Sample Size Determination

The statistical power calculation assumes that the evaluation of superiority of pooled tirzepatide 5 mg and 10 mg QW against placebo will be conducted at a 2-sided significance level of 0.05, relative to the primary endpoint (change in HbA1c from baseline at 30 weeks) in an analysis utilizing all data, on or off intervention. Additionally, it assumes a 1.1% greater mean reduction in HbA1c (placebo adjusted) for pooled tirzepatide (5 mg and 10 mg) at Week 30 visit, and a common SD of 1.5% from change in HbA1c at Week 30 visit.

Based on these assumptions, randomizing at least 90 participants in a 1:1:1 ratio to each study arm will provide 90% power to demonstrate superiority of the pooled tirzepatide 5 mg and 10 mg to placebo.

6. Supporting Documentation

6.1. Appendix 1: AESI Search Criteria

The search criteria for each AESI will be documented in an excel spreadsheet stored in Lilly Clinical Users Working Environment. The latest version of MedDRA will be used.

Pancreatitis Events

Determination of investigator-reported events will be through the Acute pancreatitis SMQ (20000022, narrow scope) and a Pancreatitis Chronic PT search of the AE database, while adjudication-confirmed pancreatitis events are found from adjudication forms.

Arrhythmias and cardiac conduction disorders

Treatment-emergent arrhythmias, arrhythmias and cardiac conduction disorders will be considered an AESI. The cardiovascular events will include clinically relevant rhythm and conduction disorders. The treatment-emergent arrhythmias and cardiac conduction disorders events will be included using the MedDRA PT contained in any of the following SMQs:

1) Arrhythmias:

- a. For symptoms: Arrhythmia related investigations, signs and symptoms SMQ (20000051), narrow and broad terms
- b. For supraventricular arrhythmias: In *Cardiac arrhythmia* SMQ (20000049), under tachyarrhythmia sub SMQ (20000054)
 - i. Supraventricular tachyarrhythmia SMQ (20000057), broad and narrow terms
 - ii. *Tachyarrhythmia terms, nonspecific* SMQ (20000164), narrow terms only; and
 - iii. Ventricular tachyarrhythmia SMQ (20000058), narrow terms only.
- 2) Cardiac conduction disorders
 - a. Conduction defects SMQ (2000056), narrow terms only; and
 - b. Cardiac conduction disorders HLT (10000032), all PTs.

Hepatic TEAEs

Treatment-emergent potentially drug-related hepatic disorders will be summarized by treatment using the MedDRA PTs contained in any of the following SMQs:

- broad and narrow terms in the *Liver related investigations*, signs and symptoms SMQ (20000008)
- broad and narrow terms in the *Cholestasis and jaundice of hepatic origin* SMQ (20000009)
- broad and narrow terms in the *Hepatitis non-infections* SMQ (20000010)
- broad and narrow terms in the *Hepatic failure*, *fibrosis and cirrhosis and other liver damage* SMQ (20000013), and
- narrow terms in the *Liver-related coagulation and bleeding disturbances* SMQ (20000015).

Acute gallbladder disease

All events of TEAE biliary colic, cholecystitis, or other suspected events related to gallbladder disease will be summarized by treatment groups by PT with decreasing frequency under the following SMQs:

- narrow PTs in Gallbladder related disorders SMQ (20000124)
- narrow PTs in Biliary tract disorders SMQ (20000125), and
- narrow PTs in Gallstone related disorders SMQ (20000127).

Renal Disorder

- Acute renal failure:
 - o Narrow terms in Acute renal failure SMQ (20000003)
- Chronic kidney disease:
 - o Narrow terms in Chronic kidney disease SMQ (20000213)

Dehydration events

• Narrow terms in Dehydration SMQ (20000232)

Major depressive disorder/suicidal ideation

AEs will be searched using MedDRA PTs from SMQs narrow scope: 20000037 (Suicide/self-injury) and 20000167 (Depression [excluding suicide and self injury]).

C-cell hyperplasia and thyroid malignancies

Thyroid malignancies and C-cell hyperplasia will be identified using MedDRA HLT for *Thyroid neoplasms malignant* and PT for *Thyroid C-cell hyperplasia*.

Hypersensitivity reactions

Analyses are based on the following:

- narrow and algorithm terms in *Anaphylactic reaction* SMQ (20000021)
- narrow terms in *Angioedema* SMO (20000024)
- narrow terms in Severe cutaneous adverse reactions SMQ (20000020), and
- narrow terms in *Hypersensitivity* SMQ (20000214).

For the Anaphylactic reaction SMQ, each term is classified by scope (narrow, broad) and by category (A, B, C, and D). All narrow terms are category A, and all broad terms are category B, C, or D. In addition to the usual narrow and broad searches, the SMQ defines an algorithm to further refine the cases of interest. For immediate analysis, the *Anaphylactic reaction* SMQ algorithm will be included. The algorithm is based upon events that occur within 24 hours. The counts and percentages of participants who experienced a TEAE for the following will be analyzed for each of the 2 time periods:

- any narrow term from any 1 of the 4 SMQs indicated above (that is, combined search across narrow of all 4 SMQs), and
- any narrow scope term within each SMQ, separately (that is, narrow SMQ search). For immediate analysis, any term from *Anaphylactic reaction* SMQ algorithm.

Injection site reactions

The ISR AE will be identified using the MedDRA PT in any of the following:

- HLT of *Injection site reaction*
- HLT of Administration site reaction NEC, and
- HLT of *Infusion site reactions*.

Diabetic Retinopathy Complications

The following PT will be used to identify TEAEs of diabetic retinopathy or maculopathy (Section 4.6.6.5):

- Non-proliferative retinopathy
- Arteriosclerotic retinopathy
- Blindness
- Blindness transient
- Blindness unilateral
- Cystoid macular oedema
- Diabetic blindness
- Diabetic eye disease
- Diabetic retinal oedema
- Diabetic retinopathy
- Diabetic uveitis
- Exudative retinopathy
- Eye laser surgery
- Fundoscopy
- Fundoscopy abnormal
- Intra-ocular injection
- Macular detachment
- Macular oedema
- Maculopathy
- Phacotrabeculectomy
- Proliferative vitreoretinopathy
- Retinal collateral vessels
- Retinal cryoablation
- Retinal detachment
- Retinal exudates
- Retinal haemorrhage
- Retinal laser coagulation
- Retinal neovascularization
- Retinal oedema
- Retinal operation
- Retinal thickening
- Retinal vascular disorder
- Retinal vascular occlusion
- Retinopathy
- Retinopathy haemorrhagic

- Retinopathy hypertensive
- Retinopathy proliferative
- Vitrectomy
- Vision blurred
- Visual impairment
- Sudden visual loss
- Visual acuity reduced
- Visual acuity reduced transiently

Diabetic Neuropathy

The following PTs will be used to identify TEAEs of Diabetic Neuropathy (Section 4.6.6.14):

- Acute painful neuropathy of rapid glycaemic control
- Diabetic autonomic neuropathy
- Diabetic mononeuropathy
- Diabetic neuropathy
- Large fibre neuropathy
- Lumbosacral radiculoplexus neuropathy
- Neuropathic arthropathy
- Small fibre neuropathy

Metabolic Acidosis, Including Diabetic Ketoacidosis

The following PTs will be used to identify TEAEs of Metabolic Acidosis, Including Diabetic Ketoacidosis (Section 4.6.6.12):

- Blood ketone body
- Blood ketone body increased
- Blood ketone body present
- Diabetic ketoacidosis
- Diabetic ketoacidotic hyperglycaemic coma
- Diabetic ketosis
- Euglycaemic diabetic ketoacidosis
- Ketoacidosis
- Ketonuria
- Ketosis
- Lactic acidosis
- Urine ketone body

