# **8.3.3.6.** Diabetic Retinopathy Complications

Visual acuity evaluation will be performed as part of the ophthalmology assessments prior to dilation. The results from this exam will be recorded on a specific eCRF. Dilated retinal fundoscopic examination for all participants will be performed by a qualified eye care professional (ophthalmologist or optometrist) between Visit 2 and Visit 3 or at a previous exam  $\leq$ 90 days of screening meeting study requirements. The results from this examination will be recorded on a specific retinopathy eCRF as a baseline measure of retinopathy.

Additional visual acuity checks and dilated fundoscopic examinations should be performed when clinically indicated by any AE suspected of worsening retinopathy, and the findings must be recorded on the retinopathy eCRF.

A follow-up visual acuity check and dilated fundoscopic examination occur for all randomized participants at Visit 19 (Week 52).

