4.6.6.5. Diabetic Retinopathy Complications

A summary of new or worsening retinopathy will be provided by treatment through Week 30 using SS1, and through Week 52 using SS2:

- An incidence of new diabetic retinopathy or diabetic maculopathy in either eye is defined as a presence of retinopathy or macular edema in either eye in those without any eye disease at baseline according to dedicated fundoscopic exam form or AE reporting.
- An incidence of worsening diabetic retinopathy or diabetic maculopathy in either eye is defined as a shift to worsening severity of eye disease reported in the follow-up fundoscopic exam form or AE reporting compared to baseline.

• The AE will be searched using predefined PTs to identify events consistent with diabetic retinopathy, diabetic macular edema, and related complications. Detailed search criteria can be found in Appendix 1.

A shift table will be presented using SS2 for double-blind and open-label periods for the results from the dilated fundoscopic exams. The table will show the proportions of participants with shifts in retinopathy status from baseline to most severe postbaseline result using categories defined on the eCRF. These are

- no retinopathy
- mild non-proliferative diabetic retinopathy
- moderate non-proliferative diabetic retinopathy
- severe non-proliferative diabetic retinopathy, and
- proliferative diabetic retinopathy.

Results from visual acuity exam reported on the eCRF will be summarized by treatment and by eyes (that is, any eye, left eye and right eye) for baseline and postbaseline visit (Week 52).

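### The SAP does not say whether a visual-symptom AE alone makes a retinopathy case, so blurred vision can be counted as incident diabetic retinopathy, chiefly at Week 30

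*SAP*

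**What the plan says.** SAP 1.1 lists the incidence of new or worsening diabetic retinopathy or maculopathy as an additional secondary endpoint, not controlled for type I error. It is to be compared with placebo at Week 30 and assessed at Week 52. Protocol Section 3 had placed it at Week 52 only.

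SAP 4.6.6.5 defines a new case: "An incidence of new diabetic retinopathy or diabetic maculopathy in either eye is defined as a presence of retinopathy or macular edema in either eye". The rule covers participants who had no eye disease when they entered, and the evidence may come from the examination form or from an AE report. Worsening is "a shift to worsening severity of eye disease reported in the follow-up fundoscopic exam form or AE reporting compared to baseline". In both definitions the form and AE reporting are alternatives.

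The same section says the AEs will be found by a predefined PT search. It describes the target loosely, as events compatible with retinopathy, macular edema and related complications. SAP Appendix 1 is firmer: "The following PT will be used to identify TEAEs of diabetic retinopathy or maculopathy (Section 4.6.6.5". The list that follows contains "Vision blurred", Visual impairment, Visual acuity reduced and Visual acuity reduced transiently. It also contains procedures such as Fundoscopy and Vitrectomy, and two retinopathies named for another cause, "Retinopathy hypertensive" and Arteriosclerotic retinopathy.

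Protocol 8.3.3.6 schedules a follow-up dilated examination at Visit 19 (Week 52). It asks for extra examinations when clinically indicated by an AE suspected of worsening retinopathy, and in that case "the findings must be recorded on the retinopathy eCRF".

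**The concern.** A broad PT list suits a search for reports to look into. Here nothing follows the search: no confirmation by examination, no adjudication, and no statement that a hit is only a candidate. Read with the either-or definition, a report of blurred vision can enter the numerator of an endpoint whose stated target is retinopathy or macular edema.

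In a trial this small, a few such reports could make up much of the reported incidence. They could suggest a retinal signal where there is none, or blur a real one by adding unrelated cases to either side of the comparison.

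**Working it through.** No figure in the plan can be reproduced for this point. The check compares the passages, counts the list, and then illustrates the size.

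**1. What makes a case.** The target in SAP 4.6.6.5 is the presence of retinopathy or macular edema. The source is the form or AE reporting. The AE source is the PT search. Appendix 1 labels the hits as TEAEs of the disease, while 4.6.6.5 speaks only of compatible events. The label in Appendix 1 makes a hit a case; the language of 4.6.6.5 makes it a candidate. Neither section says what happens when an examination has been done and disagrees. For worsening, nothing says how a symptom PT, which carries no grade of eye disease, could show a shift in its severity.

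**2. The list.** My count and classification of the 43 PTs:

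| Type | PTs |
|---|---|
| Visual symptom or visual loss (e.g. Vision blurred, Blindness transient, Sudden visual loss) | 8 |
| Procedure or investigation (e.g. Fundoscopy, Vitrectomy, Intra-ocular injection) | 8 |
| Retinopathy named for another cause | 2 |
| Diabetic uveitis | 1 |
| Named diabetic eye disease, retinopathy, retinal oedema or blindness | 4 |
| Other retinal or macular finding, including Fundoscopy abnormal | 20 |

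The first three rows give 8 + 8 + 2 = 18, and 18/43 = 42%.

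**3. Comparison within the SAP.** Section 4.6.6.3 keeps adjudicated pancreatitis apart from investigator-reported events. The measurement route to new hypertension in 4.6.4 needs two consecutive elevated readings on separate visits. The neuropathy PT list in Appendix 1 names diagnoses, not symptoms. The retinopathy endpoint has no comparable safeguard on its AE route.

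**4. Week 30.** The schedule of activities (Protocol 1.3) places the eye examination between Visits 2 and 3, at Visit 19 and at early termination. The early-termination examination is waived if the last one was within 6 months, which is about 26 of the 30 double-blind weeks when the baseline examination was done near randomization. SAP 4.1.4 rules out between-group comparison at Week 52. The only placebo comparison of this endpoint therefore rests mainly on AEs, with whatever unscheduled or early-termination examinations happen to exist.

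**5. Size.** SAP 1.2.2 gives at least 90 participants at 1:1:1, so 30 per arm and 60 on pooled tirzepatide. One case moves an arm by 1/30 = 3.3 percentage points and the pooled arms by 1/60 = 1.7. The documents give no rate for visual-symptom AEs. At an assumed rate r, the pooled arms expect 60r such participants, and the chance of at least one is 1 − (1 − r)^60:

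| Assumed r | Expected in 60 | Chance of at least one |
|---|---|---|
| 3% | 1.8 | 84% |
| 5% | 3 | 95% |
| 10% | 6 | over 99% |

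**6. Share of counted cases that would be unrelated.** Assume true incidence p, unrelated listed AEs at rate q, and independence. Observed incidence is 1 − (1 − p)(1 − q), and the unrelated share is (observed − p)/observed. With p = 5%:

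| Assumed q | Observed | Unrelated share |
|---|---|---|
| 2% | 6.9% | 28% |
| 5% | 9.75% | 49% |
| 10% | 14.5% | 66% |

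At p = 2% the shares are 50%, 71% and 83%. At p = 10% they are 15%, 31% and 47%. Both p and q are assumptions.

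**The case against.** The best defense is that this is a search and not a case definition. Appendix 1 is headed as search criteria, 4.6.6.5 asks for the presence of disease, and favoring sensitivity is a legitimate choice for safety. This shows the wording is ambiguous. It does not supply the missing step from hit to case.

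Existing displays also limit the harm. SAP 4.6.6.5 has a shift table built from examinations only, and a visual acuity summary. SAP 4.6.2 tabulates TEAEs by PT. SAP 4.6 allows a listing in place of a table when a special safety topic has few events. These stand, and they keep the point modest.

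Four stronger readings are tempting, and the documents do not support them:

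- *That the SAP counts a symptom despite a normal examination.* No sentence says so. It is an inference from the either-or rule and the absence of an override.
- *That procedure terms will inflate the count.* Protocol 10.3.1 treats the condition behind a procedure as the AE, so terms such as Fundoscopy should be rare. Visual symptoms are the likelier source.
- *That a confirming examination is required and then ignored.* Protocol 8.3.3.6 asks for one when clinically indicated by a suspected AE, so blurred vision need not trigger it. Positive findings do count, through the form. What is missing is a rule linking the examination result back to the AE.
- *That the bias runs against tirzepatide.* Visual symptoms might follow falling glucose on active treatment or high glucose on placebo. The documents do not settle which.

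**Conclusion.** The point holds as a gap in the endpoint's definition. As written, a visual-symptom AE can be counted as incident diabetic retinopathy, and two sections of the SAP differ on whether it should be. The effect is largest at Week 30, the only placebo comparison, where no eye examination is scheduled.

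The 3.3-point and 1.7-point steps follow from the planned sample size. The expected counts and unrelated shares rest on assumed rates and show a range, not a forecast. The 18 of 43 rests on my classification, and a few terms could be placed differently.

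This is an additional secondary safety endpoint without type I error control. The primary and key secondary results and the examination-only shift table are untouched. A correction is worthwhile because it is cheap and stops symptoms being reported as retinopathy.

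**What to change.** In SAP 4.6.6.5 and Appendix 1, split the PT list and state the rule from hit to case. Count a participant in the endpoint incidence if any of these applies:

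1. the fundoscopic form shows new or worse disease;
2. an AE has a PT that is itself a retinal or macular diagnosis, not attributed by name to a non-diabetic cause;
3. an AE has a symptom, visual-loss or procedure PT, and a retinopathy eCRF examination shows new or worse retinopathy or macular edema against baseline.

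Assign borderline terms, such as Diabetic uveitis and Fundoscopy abnormal, explicitly. Report the present broad-list count beside the narrow one, labelled as a sensitive search. Tabulate or list the remaining symptom, visual-loss, procedure and other-cause PTs separately, showing whether an examination was done and its result.

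The cost is SAP wording, a two-part PT list and one extra display. No new data or visits are needed. The drawback is that the narrow count loses sensitivity where no examination was done, which will be common before Week 30 and matters most for terms such as Blindness or Sudden visual loss. Keeping the broad count and the separate display leaves those reports visible.

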## 8.3.3.14. Metabolic Acidosis, Including Diabetic Ketoacidosis

Ketoacidosis, a serious life-threatening condition requiring urgent hospitalization, has been reported occasionally in participants with T2DM. Participants who present with signs and symptoms consistent with severe metabolic acidosis should be assessed for ketoacidosis regardless of presenting BG levels, as ketoacidosis may be present even if BG levels are less than 250 mg/dL.

If ketoacidosis is suspected, participant should be evaluated, and prompt treatment should be instituted. Treatment of ketoacidosis may require insulin, fluid, and carbohydrate replacement.

Lactic acidosis has been reported rarely in participants with T2DM associated with use of metformin, excessive alcohol intake, and decreased renal function. Routine bicarbonate assessment will be performed during the course of the study. If lactic acidosis is suspected, metformin, if used, should be temporarily discontinued until the resolution of the event.

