4.6.6.12. Metabolic Acidosis, Including Diabetic Ketoacidosis

Metabolic acidosis, including diabetic ketoacidosis will be captured as AESIs. The AE database will be searched using MedDRA PT to identify events consistent with metabolic acidosis, including diabetic ketoacidosis. The incidence of the resulting TEAEs will be summarized by treatment and PT using SS1 from baseline to Week 30 and using SS2 from baseline to safety follow-up (Information regarding searching criteria can be found in Appendix 1).

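### The search list for the metabolic acidosis AESI holds ketone terms and lactic acidosis, but no term for metabolic acidosis itself

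*SAP*

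**What the plan says.** SAP 4.6.6.12 states the target: "Metabolic acidosis, including diabetic ketoacidosis will be captured as AESIs". It states the method too: the adverse event database is "searched using MedDRA PT to identify events consistent with metabolic acidosis, including diabetic ketoacidosis". For the criteria it sends the reader on: "Information regarding searching criteria can be found in Appendix 1". The resulting events are summarised by treatment and PT, to Week 30 on SS1 and to safety follow-up on SS2.

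SAP Appendix 1 (6.1) then gives the list, introduced by "The following PTs will be used to identify TEAEs of Metabolic Acidosis, Including Diabetic Ketoacidosis". Twelve terms follow. Nothing in the introduction marks them as examples, and no SMQ or HLT accompanies them. The appendix also opens by saying that the criteria for each AESI will be held in a spreadsheet on the sponsor's system and that the latest MedDRA version will be used.

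Protocol 8.3.3.14 uses metabolic acidosis as the wider category: "Participants who present with signs and symptoms consistent with severe metabolic acidosis should be assessed for ketoacidosis". The same section describes lactic acidosis separately and provides for routine bicarbonate measurement.

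**The concern.** In both documents the AESI is named for metabolic acidosis, and ketoacidosis is one form of it. The list that puts the AESI into practice covers ketotic and lactic forms only. Read as written, it cannot find an event whose PT is the AESI's own heading.

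What is at stake is the completeness of one pre-specified safety summary in a paediatric trial. A reader who sees no cases in that summary would conclude that there was no metabolic acidosis. The search would support only the narrower statement that no ketone-related or lactic acidosis term was coded.

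**Working it through.** The SAP gives no figure to reproduce and no power or rate calculation applies. The check is a classification of the list against the stated target.

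**Step 1. Classify the terms in SAP Appendix 1.**

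- Ketone, ketosis or ketoacidosis (11): Blood ketone body; Blood ketone body increased; Blood ketone body present; Diabetic ketoacidosis; "Diabetic ketoacidotic hyperglycaemic coma"; Diabetic ketosis; Euglycaemic diabetic ketoacidosis; Ketoacidosis; Ketonuria; Ketosis; Urine ketone body.
- Lactic (1): Lactic acidosis.
- Metabolic acidosis or unspecified acidosis: 0.

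Total: 11 + 1 + 0 = 12.

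**Step 2. Compare with the target.** SAP 4.6.6.12 asks for events consistent with metabolic acidosis. SAP 4.6 codes events from the reported wording to MedDRA PTs, so for a search by PT the coded term alone decides whether an event is found. An event coded to a metabolic acidosis term matches none of the 12.

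**Step 3. Look for a safety net.** Other topics in Appendix 1 use SMQs or HLTs: hepatic, gallbladder, renal, arrhythmia, hypersensitivity and injection site reactions. This topic has none. Two other topics, retinopathy and neuropathy, also rely on lists of individual PTs. Both lists contain their own heading concept (Diabetic retinopathy; Diabetic neuropathy). This one does not.

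**Step 4. Ask whether such a report could arise.** Bicarbonate is in the chemistry panel (Protocol Appendix 2). Clinically relevant laboratory changes are to be reported as adverse events (Protocol 8.2.7). Where possible the investigator records the diagnosis rather than the signs (Protocol 10.3.4). A participant assessed for ketoacidosis with a negative result, and without lactic acidosis, could be recorded as having metabolic acidosis. The pathway exists, but the documents do not say how often it would be followed.

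**The case against.** Four points can be made on the other side.

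- **The event is not lost to the report.** This stands. SAP 4.6.2 summarises TEAEs by PT, with comparisons at SOC and PT level. SAP 4.6.2.2 summarises and lists SAEs. Narratives cover SAEs and permanent treatment discontinuations due to an adverse event. Abnormal laboratory findings are listed under SAP 4.6.3. A reader might infer that a metabolic acidosis event would vanish from the safety results; the documents do not support that. The gap is confined to the AESI summary.

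- **Work-up and recording rules narrow the gap.** This stands in part. Suspected severe cases are assessed for ketoacidosis, and the specific forms that the protocol names, ketoacidosis and lactic acidosis, are both on the list. Many cases would probably be recorded under a listed diagnosis. What remains is acidosis with neither diagnosis, so the right word is that events could be missed, not that they would be.

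- **The spreadsheet may already hold the term.** This cannot be excluded, because its contents are not given. But SAP 4.6.6.12 points to Appendix 1, and Appendix 1 presents its own list as the one to be used. If the spreadsheet is broader, the two sources disagree and the SAP text still needs correcting.

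- **The list is already sensitive.** Terms such as Ketonuria could bring in events that are not acidosis at all, so the net direction of error in the AESI count is not established. This stands, but over-inclusion on the ketone side does not make up for leaving out the heading concept.

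A reader might also be tempted to size the problem as one participant over an arm of 30 or a pooled 60. That ratio is the same for any missed event of any kind and says nothing about how likely a miss is here. Nor is there a mismatch between periods: the section already applies one search to both SS1 and SS2.

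**Conclusion.** The point holds as a mismatch between the name of the AESI and the list that defines it: 12 terms, none for metabolic acidosis, and no broader query behind them. An event recorded and coded as metabolic acidosis without a ketotic or lactic diagnosis could be missed by the AESI summary, while remaining in the general adverse event outputs.

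Its size cannot be given, because the documents contain no event rate. The conclusion rests on two assumptions that the documents cannot settle: that the coding dictionary has a metabolic acidosis PT separate from the 12 listed, and that the search spreadsheet does not already include it. If the second fails, the fault becomes a disagreement between the spreadsheet and Appendix 1.

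The point does not affect the primary or key secondary analyses or the type I error control.

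**What to change.** Add the metabolic acidosis PT to the list in SAP Appendix 1. If the dictionary also has an unspecified acidosis term, add it with case review, since acidosis need not be metabolic. Make the spreadsheet match, so that only one list is in force.

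If the sponsor intends the narrower search, the alternative is to rename the AESI in SAP 4.6.6.12 and Appendix 1, so that the table title says what is counted.

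The cost is one or two terms in an appendix and a spreadsheet, and possibly a few more cases to review; renaming costs a heading. Neither changes data collection, sample size or alpha. The change is best made before unblinding, so that the choice of safety terms is not made with the results in view.
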